Low Cost Optical Coherence Tomography for Point of Care

NCT03323307

Document Date: August 5, 2019

Purpose of the Study

We propose to introduce a low cost handheld retinal OCT device for retinal imaging in order to reduce the cost from currently \$40k-60k to under \$10k. We will obtain a retinal OCT scan with the prototype handheld OCT scanner in adult patients scheduled in the retina clinic at the UNC Kittner Eye Center undergoing standard OCT testing as part of their visit. This pilot study will aim to compare the data of this prototype device with data from currently available high resolution OCT machines.

Background and Significance

Optical coherence tomography (OCT) has become the gold standard for diagnosing eye diseases such as diabetic retinopathy and macular degeneration. The ability of OCT to create depth resolved, cross sectional images allows physicians to examine the various layers of the retina and see the earliest signs of disease. While OCT has seen wide adoption, the high cost of imaging systems (\$40,000-\$100,000+) has resulted in this technology being available primarily at large eye centers. However, for some patients such as advanced diabetics, travel to a central eye care facility can be a barrier to receiving needed follow up exams. In most communities, the primary eye care provider is an optometrist who may not provide OCT imaging due to the high system cost. Further, the high price of OCT systems has resulted in limited use in developing countries where the value of clinical OCT is understood, but currently systems are too expensive. To address this unmet need, we have developed a prototype OCT system with a target sales price of \$10,000 which provides system performance comparable to other entry level OCT imaging systems at a fraction of their cost. By delivering OCT imaging at this price, we seek to make OCT accessible to most clinics and at the point of care. We have spoken with ophthalmologists and optometrists who confirm the need for a low cost system in the detection and monitoring of diabetic retinopathy, glaucoma, retinopathy of prematurity, and macular degeneration.

Study Design and Procedures

The device is a standard optical coherence tomography configuration, consisting of a light source, an interferometer and a detector. Light from a superluminescent diode (SLD) is split into the reference and sample arms of the interferometer. Light in the sample arm is directed toward the eye through a scanning mirror. A 3 mm diameter beam is focused onto the retina by the eye's lens and swept across the surface as the mirror is scanned.

For this system, the light source is an SLD from Exalos, producing mean power of 3.5 mW and a center wavelength of 832.6 nm. The bandwidth is 47.6 nm, resulting in a coherence length (depth resolution) of 6.4 micrometers. After passing through the interferometer and other

optical elements, the resulting sample arm contains 0.6 mW of optical power in a 3 mm diameter beam incident on the cornea. The resulting optical power density at the cornea is $0.08 \text{ mW/mm}^2 = 0.008 \text{ W/cm}^2$

ANSI limit for maximum exposure to the eye is < 0.7 mW in the 800-900 nm range through a 7 mm pupil aperture for continuous exposure of up to 8 hours. Thus the low cost OCT device would be below this threshold with a 7 mm diameter beam. However, with the smaller beam of 3 mm, which does not fill the eye's pupil aperture, the focusing power is reduced. Therefore, the power is significantly (4-5x) below the maximum permissible exposure.

Subjects will be informed of the study when they present to the clinic for a regular clinical care visit. Besides the standard OCT which is obtained during the routine visit, OCT of both retinas will be performed using the Low Cost handheld OCT prototype. The OCT software will calculate central macular thickness as well as macular volume. [name] will compare the quality of obtained images and measurements between the standard and the new OCT device.

Subject Recruitment and Compensation

Adult patients scheduled in the retina clinic at the UNC Kittner Eye Center will be recruited.

Inclusion Criteria

- 1) At least 18 years of age at the time of examination (no upper age limit)
- 2) Patients scheduled to receive standard OCT testing as part of their visit.

Exclusion Criteria

none

Subjects will receive a \$20 stipend for their time. The subject will receive payment upon completion of the study visit.

Consent Process

All subjects will be consented by the study coordinator, and will be assured that their willingness to participate will not impact their future care at UNC. [name] will speak with potential participants at the very beginning of the visit, explain the details of the study, and answer all questions. All subjects will be assured that their participation in this study is strictly voluntary, this will be a one-time procedure adding approximately 5 minutes to the standard eye scan, and their future care with UNC Kittner Eye Center will not be impacted in any way if they decline to participate. At this point the technician will work up the patient as usual. This gives the patients about 45 minutes to think about participating in the study. Later when they are examined by [name] in a private exam room, any further questions are being answered and written consent will be obtained by the study coordinator if the patient chooses to

participate. Again, the completely voluntary nature of participation in this study will be stressed to the patient.

Risk / Benefit Analysis

Potential Risks

Potential risks include:

1. breach of confidentiality
2. side effect from study procedures and/or devices

Breach of confidentiality

Data collected as part of this study will be stored in password-protected electronic databases on password-protected servers within the Department of Ophthalmology at UNC and will be accessible only by essential study personnel. Information recorded on paper data sheets will be treated as strictly confidential and will be stored within locked files in the Department of Ophthalmology. Access to electronic and paper files will be restricted to the personnel listed on this study. Only the PI and Study Coordinator will have access to the key linking identifiers from PHI with study data.

Side Effect from Study Procedures and/or Devices

There is no known risk from the use of a retinal OCT except for some potential discomfort from the bright blue light used in the scanner.

Potential Benefits

There is no direct benefit to subjects participating in this research study. However, the benefit to society may be in lowering the cost of OCT machines, thus increasing their use in ophthalmic practices.

Alternative Treatments

There are no alternative treatments to participating in this research. It is not intended to be therapeutic, but to acquire basic scientific knowledge.

Data Analysis and Statistical Considerations

Central macular thickness and total macular volume measurements from the new OCT device will be compared with standard OCT. Every scanner has a slightly different values for "normal eyes", meaning the central foveal thickness might read 300 microns on one scanner and 280 on a different one. We will try to establish a database/values for eyes without retinal disease on the new OCT system. Given the low number of patients in this pilot study, we do not plan to compare the new scanner with existing ones statistically (we will not determine p-values). The

quality of OCT images obtained with the new OCT device will be judged as adequate or inadequate by the UNC site PI.

Data and Safety Monitoring

Reporting of Adverse Events

An adverse event is defined as any untoward medical occurrence in a clinical research subject participating in the clinical study of the OCT system. Any AE that occurs between the time a study participant signs the informed consent form and the time she or he departs the study at the end of the visit will be captured and recorded. Study participants will be instructed to contact the study site staff to report any AEs they may experience after completion of their participation. AE resolution will consist of evaluating instrument design and application to assess the potential source and implementing design changes to mitigate the risk of further AE. If necessary, AEs will be reported according to IRB guidelines.

Safety Monitoring

During the proposed trial of the OCT system, status reports will be submitted to the Duke PI from the UNC site. These reports will include all adverse events reported for the study, determined to be related or unrelated to the study protocol. The study team will meet, as needed, throughout the period of study to review any reported adverse events and address any potential safety concerns.

Data accuracy and protocol compliance

Data acquired during the clinical study will be reviewed by Duke lab personnel to assess if the data appear to be consistent with expected operating characteristics of the device. In the event that data do not appear satisfactory, a review of protocol compliance will be conducted. If the protocol has been followed, a technical inspection of the device by Duke lab personnel will be scheduled and further study will be suspended until instrument function has been verified.

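### Is the claimed 4-5x margin below the light-exposure limit contradicted by the protocol's own figures?

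*Combined protocol and SAP*

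**What the plan says.** The light-exposure argument is in Study Design and Procedures of the combined protocol and SAP. The device figure is "the resulting sample arm contains 0.6 mW of optical power in a 3 mm diameter beam incident on the cornea". The text adds a corneal power density of 0.08 mW/mm², also given as 0.008 W/cm². The limit is "ANSI limit for maximum exposure to the eye is < 0.7 mW in the 800-900 nm range through a 7 mm pupil aperture", on the basis of uninterrupted exposure lasting up to 8 hours.

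Two steps follow. The first is a direct comparison: "Thus the low cost OCT device would be below this threshold with a 7 mm diameter beam". The second credits the narrower beam actually used: "with the smaller beam of 3 mm, which does not fill the eye's pupil aperture, the focusing power is reduced". The conclusion is "Therefore, the power is significantly (4-5x) below the maximum permissible exposure". No formula or intermediate value links the second step to 4-5x, there or elsewhere.

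The risk section (Side Effect from Study Procedures and/or Devices) gives no margin. It says "There is no known risk from the use of a retinal OCT except for some potential discomfort" from the brightness of the scanner light.

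**The concern.** The conclusion is worded as a consequence of the figures before it, yet a reader who forms the natural ratios does not land between 4 and 5. Power alone gives a margin of 1.17x and diameter scaling gives under 3x. Area scaling gives more than 5x. The sign of any error would therefore depend on the scaling chosen: 4-5x is too generous on power or diameter and cautious on area.

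This is the document's only numerical multiple for light safety. It concerns a prototype aimed at both eyes of each participant, in a study with no exclusion criteria. If the multiple were wrong and an ethics reviewer relied on it, the reviewer would have a mistaken picture of how far the device sits below the limit.

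**Working it through.** **Inputs**, all from Study Design and Procedures: device power P = 0.6 mW; beam diameter d = 3 mm; limit L = 0.7 mW; reference aperture D = 7 mm; printed density 0.08 mW/mm².

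**Printed density.** P / (π d²/4) = 0.6 / 7.07 = 0.085 mW/mm² (unrounded 0.0849), or 0.0085 W/cm². To the precision printed this is 0.08 and 0.008, so the density reproduces.

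**Claimed margin, from nominal values.**

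| Scaling | Formula | Alone | Times L/P |
|---|---|---|---|
| Power only | 0.7/0.6 | 1.17 | – |
| Beam diameter (assumed) | 7/3 | 2.33 | 2.72 |
| Beam area (assumed) | (7/3)² | 5.44 | 6.35 |

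None lies in 4-5, so the claim is not reproduced from nominal values.

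**Which rows fit the argument made.** The power-only row omits the beam-size step that the text explicitly takes. Diameter scaling is stated nowhere. Area scaling is not stated either, but it matches the units in which the text reports exposure. On that row the nominal 5.44 exceeds the top of the claimed range by 5.44/5 = 1.09, or 9%, so the claim errs on the cautious side.

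**Rounding of the density.** A printed 0.08 covers 0.075 to 0.085 mW/mm². With P = 0.6 mW:

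- beam area = 0.6/0.085 to 0.6/0.075 = 7.06 to 8.00 mm²
- beam diameter = 3.00 to 3.19 mm
- aperture area = π × 7²/4 = 38.48 mm²
- area margin = 38.48/8.00 to 38.48/7.06 = 4.81 to 5.45

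This overlaps the upper part of 4-5x. Equivalently, area scaling gives 4 to 5 for a beam of 7/√5 = 3.13 mm to 7/√4 = 3.50 mm. Diameters from 3.13 to 3.19 mm agree with both the printed 3 mm and the printed density.

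**Limits of the rounding argument.** It works for area scaling alone. Multiplied by L/P, with the powers taken as exact, the range is 4.81 × 1.167 = 5.61 to 5.45 × 1.167 = 6.36, with no overlap. If 0.6 and 0.7 mW are instead treated as rounded to one decimal and the diameters as exact, the results are 1.00-1.36 (power), 2.33-3.18 (diameter with power) and 5.44-7.42 (area with power), again with no overlap.

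**A ratio that does fall in the range.** (7/3)² × (0.6/0.7) = 4.67. This is the device's corneal irradiance divided by the limit spread over a 7 mm aperture, so it describes a device figure that is higher, not lower.

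**The case for a change.** The strongest case for acting is that a safety multiple should be reproducible. On nominal figures this one is not, and the reader cannot tell whether it is cautious or inflated. If the quoted limit gives no credit for a narrow beam, the supported margin is 1.17x and the claim is 4/1.17 = 3.4 to 5/1.17 = 4.3 times too high. The only simple combination of the printed powers and diameters that lands in the range, 4.67, points the wrong way, which raises the possibility of an inverted ratio. Rounding rescues the claim only under an unstated scaling.

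Part of this stands. The derivation is absent, and showing it would be good documentation. The rest depends on facts the document does not contain. The 3.4-4.3 overstatement needs a no-credit reading of the limit, which the text's own argument rejects. Nothing identifies 4.67 as the source. The limit as quoted is a power through an aperture, and no irradiance limit is given against which 4.67 could count as an excess. The 8-hour basis also matters for context: the beam is scanned, and the Consent Process section puts the added time at about 5 minutes. The document quantifies neither effect and the 4-5x claim does not invoke them, so they do not rescue the number. They do argue against presenting 1.17x as the practical margin.

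**Conclusion.** The basis for 4-5x is not shown, but the documents do not establish that it is wrong. On area scaling the multiple is either slightly cautious (5.44x nominal) or compatible with rounding (4.81-5.45x). On power or diameter scaling it would be overstated. Choosing between these requires the form of the cited limit, which is not given, and the preference for area scaling is an inference from the text's units.

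The multiple also carries little weight. The quoted powers, 0.6 mW against 0.7 mW, put the device under the limit as quoted with no beam-size credit, and a reader can check that without the multiple. The risk section does not cite it. No procedure, eligibility rule, endpoint or analysis depends on it, and Data Analysis and Statistical Considerations plans no hypothesis tests. Deriving or deleting the parenthetical would alter nothing that is done to participants or concluded from their data. This is missing detail with no gain from a change to the plan. No exceedance of the quoted limit is shown, and nothing here proposes an exposure level.

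### Does the blue light named in the risk section mean that a light source is missing from the exposure assessment?

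*Combined protocol and SAP*

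**What the plan says.** Under Study Design and Procedures, the combined protocol and SAP describes the prototype as a standard OCT arrangement "consisting of a light source, an interferometer and a detector". The source is an SLD "producing mean power of 3.5 mW and a center wavelength of 832.6 nm". The section continues: "The bandwidth is 47.6 nm, resulting in a coherence length (depth resolution) of 6.4 micrometers". The power reaching the eye is "0.6 mW of optical power in a 3 mm diameter beam incident on the cornea".

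Exposure is compared with one benchmark: "ANSI limit for maximum exposure to the eye is < 0.7 mW in the 800-900 nm range", stated for a 7 mm pupil aperture. The section then argues that the narrower 3 mm beam puts the actual exposure 4 to 5 times below the permitted maximum. No fixation target, aiming beam or other visible light is described.

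The side-effect paragraph of the Risk / Benefit Analysis says that retinal OCT carries no known risk, with one exception: "some potential discomfort from the bright blue light used in the scanner".

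The Data Analysis section plans a descriptive comparison of macular thickness and volume with standard OCT, and an image-quality judgement by the site investigator. On testing it says "we will not determine p-values".

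**The concern.** The two sections appear to describe different lights. One gives a near-infrared diode and an exposure check confined to 800-900 nm. The other attributes the only named device effect to visible blue light, which that diode does not emit and that limit does not cover.

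There are two possibilities, and each looks uncomfortable:

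- **The prototype contains a blue source.** Its wavelength and power appear nowhere, and the exposure assessment leaves it out.
- **It contains none.** The risk section then names a light the device does not have and does not mention the beam that enters the eye.

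For an investigational eye device used on both eyes of retina-clinic patients with no exclusion criteria, an incomplete exposure assessment would matter. The question is whether the documents show that there is one.

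**Working it through.** **Inputs, all from Study Design and Procedures:** centre wavelength 832.6 nm; bandwidth 47.6 nm; stated coherence length 6.4 micrometers; 0.6 mW at the cornea in a 3 mm beam; stated power density 0.08 mW/mm²; limit 0.7 mW for 800-900 nm.

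**1. Is 832.6 nm a typing error?** For a Gaussian source, coherence length = (2 ln 2 / π) × λ² / bandwidth.

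(2 × 0.6931 / 3.1416) × 832.6² / 47.6 = 6,426 nm = 6.43 micrometers, against the stated 6.4.

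The plan's figure reproduces, so wavelength and bandwidth are consistent with each other.

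**2. Is the corneal power density consistent?** Beam area = π × 1.5² = 7.07 mm². Then 0.6 / 7.07 = 0.085 mW/mm², or 0.0085 W/cm². The stated 0.08 and 0.008 agree if truncated.

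**3. Could the diode itself be the blue light?** Half-maximum band = 832.6 ± 47.6/2 = 808.8 to 856.4 nm, wholly inside 800-900 nm.

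- Taking 500 nm as the upper edge of blue (an assumption), its distance from the centre is (832.6 − 500) / 47.6 = 7.0 bandwidths.
- With a Gaussian spectrum (an assumption), the standard deviation is 47.6 / 2.355 = 20.2 nm. Then 700 nm lies 6.56 standard deviations below the centre, and the fraction of power below it is about 3 × 10⁻¹¹.

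The answer is no.

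**4. Do the two sections exclude each other?** Set side by side:

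| Study Design and Procedures | Risk / Benefit Analysis |
|---|---|
| Describes the interferometric imaging path | States known risks of retinal OCT as a class |
| Names one source for that path | Mentions a light in a scanner, without saying which scanner |
| Does not say the unit has no other light | Does not say the light forms the image |

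The word scanner does not settle it. The Purpose section uses it for the prototype, and the Data Analysis section uses it for any OCT machine. The sentence may refer to a light in the prototype outside the imaging path, to the clinic's standard OCT, or to OCT generally. Each reading is compatible with the diode figures.

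**5. Does the stated exposure margin bear on this?** The ratio 0.6 / 0.7 = 86% might suggest a device close to its limit. The protocol makes that comparison for a beam filling the 7 mm aperture. For the 3 mm beam in use, its own conclusion is 4 to 5 times below the maximum, that is 1/5 to 1/4, or 20% to 25% of it. Both figures concern the diode alone and say nothing about a blue source.

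**6. Does it reach the results?** Thickness, volume and image quality come from the scans. No planned summary depends on which light the risk sentence means.

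**The case for a change.** The strongest case for acting is that both possibilities need a correction: an unassessed emitter in one, a misplaced risk statement in the other. The paragraph's heading concerns study procedures and devices, and the prototype scan is the procedure that the study adds to routine care. If the sentence is generic, the protocol's risk section contains nothing specific to the prototype. Nor can the light be dismissed as trivial, since the sentence itself calls it bright enough to cause discomfort.

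Part of this stands. The sections are not reconciled, and the risk sentence should say which device and which light it means.

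Three parts do not stand:

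- **A missing emitter is conjecture.** No section describes one, and a fixation light is a guess about the hardware.
- **Harm from misinforming patients cannot be shown.** The consent pages are not in the public document, so what patients were told cannot be seen.
- **The near-infrared beam is not overlooked.** It is assessed under Study Design and Procedures and found to be below the limit. A risk section reporting no known risk from it agrees with that assessment.

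**Conclusion.** The inconsistency is real but small, and it lies in the documentation. The diode's figures reproduce (6.43 against 6.4 micrometers), its band of 808.8 to 856.4 nm falls inside the range of the limit applied to it, and it cannot be the source of blue light. Beyond that, the documents show only that one risk sentence mentions a light described nowhere else. They do not show that the exposure assessment omits anything, or that the device is unsafe.

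No change to the design, measurements or analysis follows. The two sections should be reconciled at the next opportunity by stating which device and light are meant. If the sponsor confirms a visible source in the prototype, it belongs in the device description and the exposure assessment; if not, the sentence is a wording slip. In either case the effect on the thickness, volume and image-quality results is nil.

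This rests on the Gaussian spectrum and the 500 nm edge for blue, neither of which is critical given a distance of about 7 bandwidths. It also rests on reading the device description as an account of the imaging path, not an inventory of every light in the unit.

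### The pilot's aim is to compare two devices, but the plan names no estimate of bias, agreement or uncertainty and cites low numbers as the reason

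*Combined protocol and SAP*

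**What the plan says.** All references are to the combined protocol and SAP.

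- **Purpose of the Study** makes comparison the aim: "This pilot study will aim to compare the data of this prototype device with data from currently available high resolution OCT machines".
- **Study Design and Procedures** sets up paired data: "Besides the standard OCT which is obtained during the routine visit, OCT of both retinas will be performed using the Low Cost handheld OCT prototype". An unnamed role "will compare the quality of obtained images and measurements between the standard and the new OCT device"; no method is given.
- **Data Analysis and Statistical Considerations** names two continuous measures: "Central macular thickness and total macular volume measurements from the new OCT device will be compared with standard OCT". It expects devices to differ, giving as an example that "the central foveal thickness might read 300 microns on one scanner and 280 on a different one". Then, because few patients will be enrolled, "we do not plan to compare the new scanner with existing ones statistically (we will not determine p-values".

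The same section names two other outputs: values on the new device for eyes free of retinal disease, and a rating of its images as adequate or inadequate. No section gives a sample size, an SD, a paired difference, limits of agreement, an agreement index, an interval, or a rule for handling two eyes from one patient.

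**The concern.** The study's own question has no defined quantitative output. Low numbers argue against hypothesis tests, which would have little power and would not measure agreement anyway. They do not argue against estimation, because an interval is how a small study shows what it can and cannot tell.

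The two other outputs do not fill the gap. Reference values for healthy eyes describe the new device alone, and the quality rating describes its images. Neither measures how far its readings depart from the standard device in the same patient.

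An informal side-by-side look remains possible under the plan. It would leave the reader without a stated offset, a range for how far one reading may differ, or the precision of either. Since the plan itself expects scanners to read differently, the offset and its uncertainty are what a user needs to interpret a prototype value.

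**Working it through.** There is no figure in the plan to reproduce. The check asks whether paired estimation would be feasible and informative at pilot size.

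**Inputs**
- From the documents: patients scanned on both devices; two continuous measures; prototype scans of both eyes; no exclusion criteria; an illustrative offset of 300 − 280 = 20 microns.
- Assumed: n = 10, 20 or 50 patients; SD of the paired difference (SDd) 6 to 30 microns (with no exclusions, a small SD cannot be presumed); between-eye correlation of the device differences 0.3 to 0.8.

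**Formulas (one eye per patient)**
- Offset, 95% CI half-width: t(0.975, n−1) / √n × SDd
- Each 95% limit of agreement, approximate 95% CI half-width: t(0.975, n−1) × √(1/n + 1.96²/(2(n−1))) × SDd

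For n = 10, t = 2.262. The offset factor is 2.262/√10 = 0.715. The limit factor is 2.262 × √(0.1 + 3.8416/18) = 1.266.

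| n | Offset (SDd) | Offset, SDd 6 to 30 (microns) | Limit (SDd) | Limit, SDd 6 to 30 (microns) |
|---|---|---|---|---|
| 10 | 0.715 | 4.3 to 21.5 | 1.266 | 7.6 to 38.0 |
| 20 | 0.468 | 2.8 to 14.0 | 0.814 | 4.9 to 24.4 |
| 50 | 0.284 | 1.7 to 8.5 | 0.489 | 2.9 to 14.7 |

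The SD-unit columns apply equally to macular volume.

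**Against the 20-micron illustration, used only as a yardstick.** The half-width stays under 20 microns when SDd is below 20 divided by the factor:
- Offset: 28.0, 42.7 and 70.4 microns at n = 10, 20 and 50.
- Limit of agreement: 15.8, 24.6 and 40.9 microns.

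**Adequacy of the approximate interval for a limit.** Simulation with 200,000 normal samples per n gives coverage of 93.1%, 94.2% and 94.7% at n = 10, 20 and 50. The exact interval takes quantiles of the noncentral t with n−1 degrees of freedom and noncentrality 1.96√n, divided by √n. At n = 10 it runs from 1.163 to 3.801 SD. Relative to 1.96 that is −0.80 to +1.84 SD, so it is clearly asymmetric.

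**Two eyes per patient.** If both eyes of every patient are paired, treating them as independent understates the SE of the mean difference by √(1 + ρ): √1.3 = 1.14 at ρ = 0.3 and √1.8 = 1.34 at ρ = 0.8.

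**The case against.** **The sentence may rule out only p-values.** The parenthesis can be read as defining what is meant by a statistical comparison, and the section still commits to comparing thickness and volume. On that reading the plan is silent about estimates and does not refuse them. The reading is possible, and omitting p-values from a pilot is defensible. But nothing is named in their place on either reading, and the fix is compatible with both.

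**The loss is small and recoverable.** The paired data will exist, nothing forbids reporting mean differences, and no error rate or go/no-go rule is at stake. This stands, and it limits the weight of the point. It does not remove it, because an analysis that follows the plan would leave the main aim without an estimate.

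**The sizes are all assumed, and the yardstick is lenient.** This also stands. A half-width just under 20 microns means only that an observed 20-micron offset would barely exclude zero; it does not show that the offset is known well enough for use. At n near 10 the limits of agreement may be too imprecise to use, which partly supports the sponsor's caution. That is a reason to print the intervals, not to omit the estimates.

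**Conclusion.** The concern holds and should be fixed. The plan promises a device comparison, collects paired data for it, and names no paired estimate. Its stated reason supports dropping tests but not estimation, and because no sample size is given, that reason cannot be checked.

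On the assumed range, small numbers widen the intervals without preventing estimation. At 20 patients the offset is known to within 2.8 to 14.0 microns, while each limit of agreement is known to within 4.9 to 24.4. These figures assume normally distributed differences and one eye per patient, and they depend on n and SD values that the documents do not supply. The consequence is an avoidable loss of information; no efficacy claim or decision would be made wrong by it.

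**What to change.** Replace the sentence that declines statistical comparison with text along these lines:

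> No hypothesis tests will be done. For central macular thickness and macular volume, agreement will be estimated from differences (new minus standard) in eyes scanned on both devices: mean difference and 95% limits of agreement, each with a 95% confidence interval, and a Bland-Altman plot inspected for proportional bias. The numbers of patients and eyes contributing will be reported. Where both eyes of a patient contribute, the analysis will account for clustering by patient (patient random intercept, or one prespecified eye per patient if the model cannot be estimated). If more than one reference scanner model is used, estimates will also be given by model.

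Three details are worth settling in the same paragraph: the planned number of patients; whether scans rated inadequate contribute measurements; and the interval method for the limits, where the exact form is preferable at n near 10. By-model estimates should be treated as descriptive if few pairs fall in a group.

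The cost is one paragraph and a few hours of analysis, with no added patients, scans or readers. The downside is that the intervals will be visibly wide, and at n near 10 the limits of agreement may be too imprecise to use.

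### Prototype image adequacy is a yes/no grade with no stated criterion, no planned masking and no rule that it come before the comparison with the standard scan

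*Combined protocol and SAP*

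**What the plan says.** The combined protocol and SAP describes two assessments of image quality.

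- *Data Analysis and Statistical Considerations* sets a binary grade for the prototype: the "quality of OCT images obtained with the new OCT device will be judged as adequate or inadequate by the UNC site PI". No criterion follows.
- *Study Design and Procedures* sets a comparison of the two devices: a person whose name is removed "will compare the quality of obtained images and measurements between the standard and the new OCT device".

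The same section makes a reference scan available for every participant: "Besides the standard OCT which is obtained during the routine visit, OCT of both retinas will be performed" with the prototype.

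On analysis, the plan is descriptive. "Given the low number of patients in this pilot study", it says, "we do not plan to compare the new scanner with existing ones statistically (we will not determine p-values"). No sample size, adequacy target or decision threshold is given.

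**The concern.** A binary quality grade is informative only if the reader of the report knows what was required for a pass and what the grader could see when giving it. The plan settles neither.

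This matters because of the setting for which the device is intended. *Background and Significance* describes clinics that cannot afford OCT, where a user would have no second scan to consult. If the grader has already seen the standard scan of the same eye, or knows the diagnosis, the grade may partly reflect that knowledge. The reported rate would then describe how the image reads alongside a reference, which is a different quantity from how it reads alone.

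Since no hypothesis tests are planned, the descriptive results are the study's entire output. Without a written criterion, another reader or a later study could not reproduce the adequacy rate or set its own rate against it.

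**Working it through.** The plan gives no figure for adequacy, so there is nothing to reproduce. The check is a reading of the whole document on three questions.

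**1. Is adequate defined?** No. The document contains no landmark, layer-visibility requirement, signal threshold, segmentation rule, grading scale or reference image. This follows from the text without inference.

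**2. Is the grader shielded from other information about the eye?** No such step is described: no masking, coded images, random reading order, second reader or repeat read. The passages that bear on access are these.

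- The standard scan exists for every participant (*Study Design and Procedures*).
- Under *Breach of confidentiality*, "Only the PI and Study Coordinator will have access to the key linking identifiers from PHI with study data". The document mentions both a Duke PI and a UNC site PI and does not say which is meant here.
- Under *Consent Process*, patients are seen by a study person: "Later when they are examined by [name] in a private exam room". The name is removed, so the text does not show whether this is the site PI.

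Together these show that access is possible and that nothing rules it out. They do not show that grading takes place with the other information in view.

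**3. Is the order of the two quality assessments fixed?** No. Nothing says that the adequacy grade must come before the side-by-side comparison.

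**A possible safeguard.** Under *Data accuracy and protocol compliance*, "Data acquired during the clinical study will be reviewed by Duke lab personnel". The stated purpose is to check that the device is performing as expected. It is not described as an adequacy grade or a second read.

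**Why the direction cannot be fixed.** Let *a* be the proportion adequate when images are read alone, *u* the fraction of inadequate reads that outside knowledge raises to adequate, and *d* the fraction of adequate reads lowered because the prototype looks poor beside a better scan. Then

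reported rate = *a* + (1 − *a*)*u* − *a*·*d*.

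All values below are assumptions for illustration, with *a* = 0.70. None comes from the documents.

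| *u* | *d* | Reported rate |
|---|---|---|
| 0 | 0 | 0.70 |
| 1/3 | 0 | 0.70 + 0.30/3 = 0.80 |
| 1/2 | 0 | 0.70 + 0.30/2 = 0.85 |
| 0 | 1/3 | 0.70 − 0.70/3 = 0.47 |

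The upward shift at *u* = 1/3 is cancelled if *d* = 0.10/0.70 = 0.14. The shift at *u* = 1/2 is cancelled if *d* = 0.15/0.70 = 0.21. Modest downgrading by contrast is therefore enough to remove or reverse the inflation, and the documents give no information on either fraction.

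**The case against.** The strongest reply is that this is a small descriptive pilot. Its stated purpose is to compare prototype data with data from existing machines, no decision turns on the adequacy rate, and stand-alone use at the point of care is background motivation and not a stated objective. That is a fair limit on how serious the point is. It does not remove it, because a descriptive rate still needs a defined meaning and the remedy adds no patients, scans or readers.

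Four stronger readings are tempting and are not supported.

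- *The site PI is unmasked.* A reader might infer this from the linking key and the same-visit examination. The plan is silent on masking, the names are removed, and the PI holding the key is not identified by site. What can be said is that no masking is planned.
- *The bias favours the prototype.* Prior knowledge of a lesion could help a reader recognise it in a poor image. But the plan asks for image quality, not lesion recognition, and viewing a high-resolution scan alongside could equally make the prototype look worse.
- *This is the only quality assessment.* The device-to-device comparison is a second one, although it has no stated scale.
- *Any bias would be undetectable later.* Study data are kept in electronic databases. If the images are among them, which the plan does not state, a later masked re-read could reveal a shift.

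**Conclusion.** The point holds as a gap in the design of the grading. There is no criterion, no planned masking and no fixed order relative to the comparison with the standard scan. Consequently the adequacy rate may not reflect whether a prototype image is usable by itself. The missing criterion and the missing order are plain from the text. The effect on the rate is only a possibility, and it depends on whether the grader in fact sees the standard scan or knows the diagnosis. Its direction and size cannot be determined from the documents.

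This is a worthwhile, inexpensive improvement to a descriptive pilot. It does not undermine the study as a whole and has no bearing on participant safety.

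**What to change.** Add one paragraph to *Data Analysis and Statistical Considerations* covering three things.

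1. **Masked reading.** Export the prototype images under study codes. The same site PI grades them in random order, without patient identity, diagnosis, standard scan, or thickness and volume values.
2. **Order.** Each grade is locked before any side-by-side comparison with the standard scan.
3. **Criterion, fixed before grading.** Tie it to the measurements that the study reports, central macular thickness and macular volume. For example, an image is adequate if the fovea lies within the scan and the signal is sufficient to locate the retinal boundaries over the measured area. Boundary disruption caused by disease should not count as inadequate. Participants come from a retina clinic with no exclusion criteria, so a rule that demanded unbroken boundaries would score disease as device failure. Wording the rule in terms of signal also helps the grader apply it without knowing the diagnosis.

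The cost is coding and shuffling files, and grading in a batch. No reader, scan or patient is added. The adequacy rate may come out less favourable. Masking will be imperfect if the PI recognises distinctive eyes, which is a realistic limitation with few patients and should be acknowledged in the report.
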